SECONDARY OBJECTIVES	
 ▪ To compare metastasis-free survival for pancreatic patients following chemotherapy +/- SBRT. ▪ To compare the one year progression free survival for patients treated with mFFX +/- SBRT. ▪ To determine the overall survival for patients treated with mFFX +/- SBRT. ▪ To determine local progression-free survival for patients treated with mFFX +/- SBRT. ▪ To evaluate acute (within 3 months of treatment) grade 2 or greater gastritis, fistula, enteritis, or ulcer and any other grade 3-4 gastrointestinal toxicity within 3 months of treatment. ▪ To evaluate the utility of FDG-PET for treatment planning and estimation of progression free survival. ▪ To identify new biomarkers in pancreatic cancer.15% ▪ ▪ To evaluate the quality of life before and after therapy for patients treated with mFFX +/- SBRT.
HYPOTHESES	Systemic chemotherapy followed by radiotherapy improves overall survival in patients with locally advanced pancreatic cancer. Recent clinical studies have shown that FOLFIRINOX chemotherapy is more effective than gemcitabine as first-line treatment in patients with metastatic disease. Similarly, aggressive local radiotherapy in combination with systemic chemotherapy has also been demonstrated to improve overall survival. We hypothesize that optimizing local radiotherapy following aggressive systemic chemotherapy will further improve overall survival.

STUDY DESIGN	Multi-center phase III randomized study anticipated to accrue approximately 172 patients total at all participating institutions.
---------------------	---

SUMMARY OF SUBJECT ELIGIBILITY CRITERIA

Inclusion:

[figure not shown]
- Histologically confirmed adenocarcinoma of the pancreas.
- Determined unresectable by a pancreatic cancer surgeon or a multi-disciplinary or gastrointestinal oncology Tumor Board
- Stable or better disease on re-staging scans following induction mFOLFIRINOX.
- Typically, pancreatic tumors must be less than 8.0 cm in greatest axial dimension at the time of treatment planning but final determination of eligibility will be based upon satisfying the radiation normal tissue constraints as specified below in section 6.1.3 Radiation Treatment Planning
- No prior systemic therapy EXCEPT patients may be consented and enrolled if they have already started mFOLFIRINOX for up to four cycles.
- ECOG 0, 1, or 2 (see Appendix II).
- Acceptable organ and marrow function (as defined in protocol section 3.1).
- Ability to understand and the willingness to sign an informed consent form.
- Life expectancy >6 months.

Exclusion:

- Metastatic disease.
- Children/Age<18 (rarely occurs in this age group)
- Prior radiotherapy to the upper abdomen/liver.
- Patients who received chemotherapy for pancreatic cancer other than up to 4 cycles of mFOLFIRINOX as noted above.
- Uncontrolled illness including, but not limited to, ongoing or active infection (or infections requiring systemic antibiotic treatment), symptomatic congestive heart failure, unstable angina pectoris, cardiac arrhythmia, or psychiatric illness/social situations that would limit compliance with study requirements.
- Any concurrent malignancy other than non-melanoma skin cancer, non-invasive bladder cancer, or carcinoma in situ of the cervix. Patients with a previous malignancy without evidence of disease for > 5 years will be allowed to enter the trial.
- Pregnant and breastfeeding women are excluded; as well as women of child-bearing potential who are unwilling or unable to use an acceptable method of birth control (hormonal or barrier method, SE of

PROCEDURES	Optional: Pancreatic biopsies obtained at the time of fiducial placement or in a separate procedure, and blood collected for biomarker analysis pre-and post-treatment.
STATISTICAL CONSIDERATIONS	See statistics section.

SCHEMA

1. OBJECTIVES

1.1. Primary Objective

- To compare the median progression-free survival between arm 1 (mFOLFIRINOX) vs arm 2 (mFOLFIRINOX+SBRT).

1.2. Secondary Objectives

- To compare metastasis free survival for pancreatic patients following chemotherapy +/- SBRT.
- To compare the one year progression-free survival for patients treated with mFFX +/- SBRT.
- To determine the overall survival for patients treated with mFFX +/- SBRT.
- To determine local progression-free survival for patients treated with mFFX +/- SBRT.
- To evaluate acute (within 3 months of treatment) grade 2 or greater gastritis, fistula, enteritis, or ulcer and any other grade 3-4 gastrointestinal toxicity within 3 months of treatment.
- To evaluate the utility of FDG-PET for treatment planning and estimation of progression free survival.
- To identify new biomarkers in pancreatic cancer.
- To evaluate the quality of life before and after therapy for patients treated with mFFX +/- SBRT.

2. BACKGROUND

2.1 Natural History and Management of Pancreatic Cancer

Every year in the United States, there are more than 30,000 newly diagnosed cases of pancreatic cancer. Despite aggressive combined modality treatment approaches, the five-year survival of this disease remains less than 5%(1). Clearly, more innovative treatments are needed to improve overall survival in this group of patients.

Surgical resection is considered to be the only treatment option with curative potential(2). However, the majority of pancreatic cancer patients do not have resectable disease at presentation. More than 85% of patients have locally advanced or metastatic disease when initially diagnosed.

Since the late 1990's, first-line chemotherapy for locally advanced/metastatic pancreatic cancer has been gemcitabine, a nucleoside analog. In the pivotal trial for which the FDA approved this drug, patients treated with gemcitabine had a modest improvement in survival compared to patients treated with 5-fluorouracil (5FU)(3). The median survival was improved from 4.41 months to 5.56 months. However, nearly 25% of patients receiving gemcitabine were noted to have a clinical benefit compared to 5% of patients receiving 5FU. In a recent meta-analysis, the addition of platinum analogs to gemcitabine demonstrated a survival benefit in patients with a good performance status. However, additional studies are necessary to determine which therapeutics are best combined with gemcitabine(4).

More recently, Conroy et al reported that a non-gemcitabine containing chemotherapy regimen, FOLFIRINOX (5FU, leucovorin, irinotecan, oxaliplatin), provided a significant survival benefit compared to gemcitabine (30) in patients with metastatic pancreatic cancer. Although there was increased toxicity in those patients treated with FOLFIRINOX, this was the first randomized study showing a clinically significant advancement in the treatment of patients with advanced pancreatic cancer since gemcitabine was approved by the FDA. We hypothesize that more aggressive systemic chemotherapy followed by intensive local radiotherapy will improve overall survival in patients with locally advanced pancreatic cancer.

In a single arm multi-center (Stanford University, Johns Hopkins University, Memorial Sloan Kettering) phase II study in locally advanced pancreatic cancer, we have previously shown that integrating stereotactic body radiotherapy (SBRT, 33 Gy in 5 fractions) with systemic gemcitabine chemotherapy resulted in a 1 year freedom from local progression of 78% and a median overall survival of 13.9 months (Herman et al, Cancer 2014). There was minimal toxicity associated with SBRT and the entire radiotherapy course was delivered in 1 week. Shortening the duration of radiotherapy from 5-6 weeks (conventional IMRT) to 1 week (SBRT) minimizes any delay in the administration of systemic chemotherapy.

Another study in locally advanced pancreatic cancer compared full-dose gemcitabine (1000 mg/m²) alone to a lower dose of gemcitabine (600 mg/m²) combined with standard fractionated radiation (50.4 Gy over 5.5 weeks). Although the study was closed prior to reaching its planned accrual, there was a significant improvement in survival with combined gemcitabine and radiation compared to gemcitabine alone(5), suggesting that the addition of local radiation therapy in pancreatic cancer confers a further survival advantage to systemic chemotherapy. Objective responses were observed in 2.7% in the gemcitabine alone arm (95% CI [0.09%, 14.1%]) and 8.8% in the combined arm (95% CI [1.9%, 23.7%]). In this trial, the dose of gemcitabine was reduced to 600 mg/m² with radiation and patients required a 4-week break prior to resuming full dose gemcitabine. Grade IV toxicity, principally gastrointestinal and hematologic, was more common in the combined group (41.2 vs. 5.7%; p<0.0001). Although there was an improvement in survival, patients who received combined chemoradiation had substantially more toxicity when compared to gemcitabine alone. Because of the highly conformal and precise nature of SBRT, we hypothesize that this radiotherapy approach will improve local control and decrease radiation-related toxicity in patients with locally advanced pancreatic cancer.

Here, we will conduct a multi-institutional randomized trial to compare the effects of chemotherapy alone versus chemotherapy and SBRT in patients with locally advanced pancreatic cancer. All patients will receive a modified FOLFIRINOX regimen prior to and

following radiotherapy. The primary endpoint will be progression-free survival.

2.2 Rationale for SBRT for Pancreatic Cancer

Radiation therapy is a widely accepted treatment for pancreatic cancer. The Gastrointestinal Tumor Study Group (GITSG) carried out a series of landmark studies demonstrating the effectiveness of radiation therapy as both adjuvant and definitive treatment in pancreatic cancer(6, 7). Modern radiation treatments have increasingly used conformal fields and dose escalation to enhance tumor control(8, 9). Efforts to increase radiation dose to the pancreatic tumor without risking normal tissue injury have generally required relatively invasive techniques such as interstitial implantation of radioactive metals or intraoperative radiotherapy (IORT)(10, 11). Historically, the local control rates for conventionally fractionated radiotherapy have ranged from 25-50%. Local progression of pancreatic cancers can result in considerable morbidity, including gastric outlet obstruction and pain (12).

The mortality rate for pancreatic cancer approaches 100%. Current therapies provide only partial palliation of symptoms and slight prolongation of survival. Better treatment is clearly needed. SBRT has the potential of significantly improving local progression free survival, which could translate into both more effective palliation and longer patient survival. Koong *et al.* previously used the Cyberknife™ stereotactic radiosurgery system to demonstrate that a single dose of 25 Gy stereotactic body radiotherapy was feasible to administer in patients with locally advanced pancreatic cancer(13). Furthermore, this dose of radiation resulted in nearly 100% local progression-free survival and effectively palliated symptoms related to the local growth of pancreatic tumors. Based upon this study, these investigators also completed a phase II study assessing the efficacy of combining a standard five-week course of chemoradiotherapy followed by a stereotactic radiosurgery boost to the primary tumor in patients with locally advanced pancreatic cancer. In this cohort of 19 patients, 100% of tumors were without local progression. However, all patients eventually developed metastases with a median time to progression of 5.5 months (Koong et al, IJROBP 2005).

Another phase II study treated locally advanced pancreatic cancer patients with gemcitabine followed by 25 Gy of SBRT delivered with Cyberknife and maintenance gemcitabine chemotherapy. In this study, the excellent progression free survival was confirmed from previous studies (81%). The median overall survival was 11.4 months, median time to progression was 9.7 months and 1 year survival was 50%(14). There were no significant acute GI toxicities however, of the 15 patients alive >6 months after SBRT, 7 (47%) experienced Grade 2 or greater GI toxicity, with 2 (13%) of the 15 experiencing Grade 3 or greater GI toxicity.

More recently, another phase II study of 25 Gy in a single fraction using a linac-based approach (Trilogy™, Varian Medical Systems, Palo Alto, CA) integrated with gemcitabine chemotherapy resulted in a 50% overall survival at 1 year and a 94% freedom from local progression at 1 year. Four patients (15%) developed Grade 2 ulcers and 1 patient (5%) developed a duodenal perforation (Schellenberg et al, IJROBP 2011).

Recently, we completed a multi-center phase II trial demonstrating the efficacy of SBRT (33

Gy in 5 fractions) in combination with gemcitabine chemotherapy. No significant toxicities were observed and median overall survival was 18 months. These data compare favorably to other studies reported in the literature. Based upon these promising data, we hypothesize that adding SBRT to a more aggressive systemic chemotherapy (FOLFIRINOX), will result in further improvement in OS in patients with locally advanced pancreatic cancer.

The proposed randomized study is a logical extension of the previously reported studies and will establish the efficacy of adding SBRT to FOLFIRINOX chemotherapy. Our prior multi-center phase II experience demonstrated the feasibility and efficacy of this approach in patients with locally advanced pancreatic cancer.

2.3 Quality of Life Assessment

The major potential benefit of combining SBRT with chemotherapy for locally advanced pancreatic tumors is to improve local control and palliation of symptoms related to local progression of these tumors. In addition, radiosurgical ablation of the primary tumor can theoretically prevent distant seeding from the pancreatic tumor itself. Ultimately, these improvements in the treatment of pancreatic cancer may translate into an improved quality of life and overall survival.

Quality of life will be assessed using The European Organization for Research and Treatment in Cancer quality of life core cancer questionnaire with the pancreatic cancer module (EORTC QLQ C-30/ PAN26). The European Organization for Research and Treatment in Cancer Quality of Life Questionnaire (EORTC QOL-C30) is a multidimensional, 30-item questionnaire which assesses five functional scales (physical, role, cognitive, emotional and social), three symptom scales (fatigue, pain and nausea/vomiting), a global health /QOL scale, as well as 6 single items (18). The EORTC QLQ-PAN26 supplements the core questionnaire with 26 items specific for patients with pancreatic cancer (19, 20). These instruments have been validated in patients receiving treatment for metastatic and resected pancreatic cancer and are sensitive to identify treatment related changes in quality of life. The quality of life of patients in this study will be directly compared between the 2 randomized arms. These questionnaires were also used in our previous phase II multi-institutional study evaluating SBRT and gemcitabine in patients with locally advanced pancreatic cancer.

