7.2 Follow-up

All patients will be monitored with clinic visits, labs, and serial imaging (CT or MR scans and PET/CT if possible), and other tests as needed.

Patients deemed resectable at any time during follow-up may proceed to surgery. These patients will be withdrawn from the protocol and followed for survival.

Patients will have consultations in the first year every three months following study treatment as defined in the Study Calendar (Section 14); a follow up at 4-6 weeks is optional and may be done to assess subject's resectability, or if clinically indicated by study PIs or patient's treating physician.

For years 2 and 3, follow-up is recommended every 6 months, or until death or study withdrawal (due to progression, patient withdrawal, or noncompliance as defined in Section 7.5 Criteria for Removal from Study). Follow up intervals may be more frequent as indicated clinically. In the event of intolerable toxicity from mFFX, subjects will still be followed per protocol although chemotherapy may be altered or discontinued, the decisions of which will be left to the treating Medical Oncologist. Visits should include:

- Consultation with physical examination
- Labs: CBC, CMP, CA199. CEA and research bloods are optional.
- Scans: CT or MR and PET/CT if possible (PET/CT is recommended at 3 month follow-up visit but is not required)
- QOL (Quality of Life) Assessment with EORTC QLQ C-30 / PAN26 survey
- Adverse Event (AE) evaluation
- Concomitant Medications: PPIs and pain medications as applicable
- Other tests as appropriate.

Patients who remain on-study will be followed until death and cause of death should be obtained when possible.

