14. STUDY CALENDAR

Activity	Induction Chemotherapy				Study Treatment	Follow-up (Time From Completion of Study Treatment) ^j							
	Screening	Study Enrollment	Induction Chemo / mFFX ^g	Re-staging ^c		SBRT ^d	mFFX 2 cycles ^f	4-8 wks ^k	3 ^j mos	6 ^j mos	9 ^j mos	12 ^j mos	Yr 2-Q 6 ^j mos
Biopsy	X				R								
Negative Pregnancy test ^a	X				A								
Consultation	X	X	X ^g		N			X ^k	X	X	X	X	X
ECOG PS	X	X			D			X ^k	X	X	X	X	X
Labs: CBCD, CMP, CA19-9 (CEA optional)	X	X ^b	X ^g		O		X ^h	X ^k	X	X	X	X	X
Study/research labs ⁱ (optional)		X ⁱ			M		X ⁱ	X ^k	X ⁱ	X ⁱ	X ⁱ	X ⁱ	X ⁱ
Eligibility		X			I								
Informed Consent		X			Z								
Study Registration		X			E								
QOL		X						X ^k	X	X	X	X	X
Scan: CT or MR	X			X ^c				X ^k	X	X	X	X	X
PET/CT ^e	X ^e								X ^e				
AE evaluation						X	X ^h	X ^k	X	X	X	X	X
Seed placement						X							
Meds: PPI and pain meds ^j								X ^k	X	X	X	X	X
Sim/setup scans						X							
SBRT						X ^d							
Maintenance mFOLFIRINOX ^{fh}								X-----X ^{fh}					

^a Pregnancy test by urine or serum, for women who are not post-menopausal as defined in Appendix III.

^b Labs should be done within 30 days of eligibility confirmation.

^c Re-staging scan should be done within 2 weeks following completion of induction mFOLFIRINOX cycles.

^d SBRT should begin within 4 weeks of simulation and 8 weeks of the last chemotherapy; dose is 40 Gy (8Gy in 5 fractions).

^e PET-CTs are recommended but not required; if only 1 follow-up PET-CT is possible, recommendation is at 3 months.

^f mFOLFIRINOX should resume within 8 weeks after study treatment, and any breaks between chemotherapy cycles should not exceed 8 weeks. Patients may continue on maintenance mFFX as tolerated or per clinical judgment of treating physician.

^g Induction chemo/mFFX prior to enrollment is allowed through the 4th cycle of mFFX. No more than 4 cycles are allowed prior to randomization. The re-staging scan could be done within 2 weeks of completion of the chemotherapy cycle; records from labs and clinic visits are not required; mFFX infusion records should be collected.

^h Labs during mFFX cycles are as per institutional standard or treating Medical Oncologist. AEs should be assessed with each cycle of mFFX.

ⁱ Study labs are optional and for research purposes as explained in Section 12. Correlative/Special Studies; and may be drawn if patient agrees to this in the consent form.

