- j Follow-up appointments 1 month before or after will be permitted, e.g. for 6-month follow-up, visit, labs, scan and QOL surveys can be done at 5-7 months.
- k 4-6 week follow-up visit and corresponding activities are *optional* and may be added if clinically indicated.

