17.4 Plan of Analysis

Demographic and clinical characteristics of patients and the characteristics of treated lesions (volume, location, and modality) will be summarized by means, medians, standard deviations, ranges and proportions as applicable.

Time to event outcomes (overall survival, metastasis free survival, and progression free survival) will be summarized using Kaplan-Meier curves and medians with 95% confidence intervals calculated using Greenwood's formula. Cox proportional hazards models will be used to compare treatment groups and to assess risk factors (e.g. biologic markers and PET volume). The effect of site will be tested in the Cox models; the effect of whether or not the patients received Leucovorin will also be tested in the Cox models. The level of response (and other categorical outcomes) will be tabulated at each follow-up interval. Logistic regression and Cox models will be used to assess the proportion with a response category depending upon the level of censoring prior to the annual visit.

The measurements of the volume of the pancreatic tumors based upon CT and PET-CT scans will be compared using paired t-tests or Wilcoxon signed-rank tests as appropriate. The agreement between pancreatic tumor measurements will be compared among the three institutions using correlation coefficients, percentage agreement, and inter-correlation coefficients.

Quality of life outcomes will be assessed at each time interval and compared using the recommended guidelines from the module. Differences in QOL for the two treatment groups will be explored using a repeated measures model in order to account for the within-patient correlation. Special interest will be placed on exploring the aspects of QOL which are known to be impacted by SBRT.

At this time all research on biomarkers for disease progression is exploratory. The goal is to potentially identify biomarkers that are associated with disease progression. Should any biomarkers be identified, their impact on the time to event outcomes will be summarized using Kaplan Meier curves and they will be tested using Cox proportional hazards models.

Quality of life at each interval will be calculated and compared using the recommended guidelines from the module (available by E-mail: [contact]). Efficacy outcomes with repeated measurements over time (e.g. quality of life) will be analyzed using a generalized estimating equation (GEE) approach to account for within-patient

correlation.

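### Quality-of-life forms from the optional 4–6 week visit come from a health-selected subset, and Section 17.4 should keep them out of the between-arm comparison (minor)

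*Combined protocol and SAP*

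**What the plan says.** Section 2.3 states the intention: "The quality of life of patients in this study will be directly compared between the 2 randomized arms". Section 17.1.2 lists quality of life (QOL) among the secondary endpoints. Section 17.4 carries the intention out: "Quality of life at each interval will be calculated and compared using the recommended guidelines from the module". It also specifies a repeated-measures model for the difference between the two groups and a generalized estimating equation (GEE) for outcomes measured repeatedly. It excludes no interval and states no weighting or missing-data method for QOL.

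The Study Calendar (Section 14) schedules the QOL form at enrollment, then in a first follow-up column headed 4–8 weeks, then at 3, 6, 9 and 12 months and in year 2. The SBRT and mFFX treatment columns have no form. The clock for these columns is "Follow-up (Time From Completion of Study Treatment".

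The first follow-up cell carries footnote k: "4-6 week follow-up visit and corresponding activities are *optional* and may be added if clinically indicated". Section 7.2 gives the reasons for holding the visit: "a follow up at 4-6 weeks is optional and may be done to assess subject's resectability, or if clinically indicated by study PIs". The three-monthly visits are worded differently, as routine: "Patients will have consultations in the first year every three months following study treatment". The visit content in Section 7.2 includes "QOL (Quality of Life) Assessment with EORTC QLQ C-30 / PAN26 survey".

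**The concern.** A visit held because a patient might be resectable tends to bring in patients who are doing well. A visit held for clinical need tends to bring in patients who are doing badly. Either way, who fills in a form at this interval is related to what the form measures. This is not dropout: it concerns patients who are still on study and will complete the 3-month form.

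Section 17.4 treats the interval like any other. An unweighted GEE relies on missingness being unrelated to the outcome given the covariates in the model, and here the schedule itself ties collection to health. If the arms use the visit to different extents or for different reasons, the early comparison could show a difference in either direction when SBRT has no effect on QOL. That difference would also feed into the repeated-measures estimate.

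Some features of the trial make unequal use plausible:
- No blinding is described, and the visit is discretionary.
- SBRT must be given at a participating site (Section 6.2), while chemotherapy may be given in the community (Section 7.1).
- The visit is timed from completion of study treatment, which has no evident date in an arm that goes straight on with mFFX (Section 5.3).

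None of these shows that attendance does differ.

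**Working it through.** **No plan figure to reproduce.** The documents state no sample size, power or expected attendance for QOL. The 91% power in Section 17.3.2 concerns progression-free survival and is not at issue.

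**Step 1: the passages side by side.**
- Comparison at each interval, no exception: Section 17.4.
- First post-treatment form tied to an optional visit: Section 14, footnote k.
- Named reasons for that visit are related to health: Section 7.2.
- Form at 3 months and later not optional: Sections 7.2 and 14. Footnote j allows one month either side, so the 3-month form may be completed at 2 to 4 months.

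Only the first interval is affected by the optional visit.

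**Step 2: size at that interval.** Everything here is assumed except the 86 per arm (Section 17.3.2). Scores are normal with SD 20 and no true arm difference. A share *a* of an arm attends, and the tendency to attend has correlation −ρ with QOL, so that worse QOL makes attendance more likely, by the same rule in both arms. The mean shift among attenders is

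shift = −20 · ρ · φ(c) / a, with c the (1 − a) quantile of the standard normal.

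Worked case, ρ = 0.4, 60% v 30%: φ(c) is 0.3863 and 0.3477. The shifts are −20 × 0.4 × 0.3863 / 0.6 = −5.2 and −20 × 0.4 × 0.3477 / 0.3 = −9.3. The apparent difference is 4.1 points.

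| Attendance | ρ = 0.2 | ρ = 0.4 | ρ = 0.6 |
|---|---|---|---|
| 30% v 30% | 0 | 0 | 0 |
| 50% v 40% | 0.7 | 1.3 | 2.0 |
| 50% v 30% | 1.4 | 2.9 | 4.3 |
| 60% v 30% | 2.1 | 4.1 | 6.2 |
| 70% v 30% | 2.7 | 5.3 | 8.0 |

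Entries are points. If better QOL drives attendance in both arms, the signs reverse and the sizes stay the same. A logistic selection model agrees closely. At an odds ratio of 2 per SD it gives 1.3 points for 50% v 40% and 3.9 for 60% v 30%; at an odds ratio of 1.5, 50% v 40% gives 0.8.

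**Step 3: false-positive rate at that interval.** The standard error of the difference is 20 · √(1/(86a₁) + 1/(86a₀)). For 70% v 30% it is 4.7 points. With biases of 2.7, 5.3 and 8.0 points, a nominal 5% two-sided test rejects about 9%, 20% and 39% of the time. For 50% v 40% the rates are about 5%, 6% and 7%.

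**Step 4: the pooled estimate.** Assume four complete later visits (3, 6, 9 and 12 months), visit fitted as a factor, one common arm effect and working independence. Each visit is then weighted in proportion to n₁n₀/(n₁ + n₀).
- 70% v 30%: the first visit counts 0.7 × 0.3 / 1.0 = 0.21, and the later four count 4 × 0.5 = 2.0. Its weight is 0.21 / 2.21 = 0.095, so 8.0 points become about 0.8.
- 60% v 30%, ρ = 0.4: the weight is 0.2 / 2.2 = 0.091, so 4.1 points become about 0.4.

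Dropout at later visits would raise these somewhat.

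**The case against.** **One rule covers both arms.** A reader might infer that the early comparison is selected by arm, because re-assessment for surgery seems natural after SBRT while a control patient simply continues chemotherapy. No section says so. Sections 5.2 and 7.2 open surgery to all patients at any time, SBRT patients also return to mFFX, and the optional visit has the same wording for everyone. This stands: a difference between arms is a risk only.

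**The largest figures need an unsupported assumption.** If attendance selected better health under SBRT and worse health under control, each doubling the odds per SD with half of each arm attending, the apparent difference would be about 12.5 points (twice 6.25). Nothing in the documents supports selection in opposite directions, so that figure should not be used to size the problem.

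**The early period is not singled out.** A reader might take the special interest declared in Section 17.4 as directed at the first weeks. It names aspects of QOL affected by SBRT, with no time window. The 3-month form is scheduled for all on-study patients, and adverse events are assessed separately during SBRT and at each mFFX cycle. It would be wrong to say that early effects go wholly unmeasured.

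**The stakes are modest.** QOL is a secondary endpoint, and Section 17.4 describes the modelled arm comparison as exploratory. This too stands, and it sets the severity.

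What the objection does not remove is the plain reading: as written, the plan tests an interval whose forms come from patients called in for health-related reasons.

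**Conclusion.** The point holds as a minor one. Following Section 17.4 as written means testing, and modelling, forms from a health-selected subset at the first post-treatment interval. The comparison there is biased only if attendance or its reason differs by arm, which the documents neither show nor rule out.

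Under assumed same-direction selection and SD 20, the bias is zero with equal attendance and equal selection, about 1 point at 50% v 40%, about 4 points at 60% v 30%, and about 8 points in the most unequal, strongest-selection case tried. The pooled estimate moves by less than 1 point in the cases worked, given complete later forms. These sizes rest on assumed attendance, selection strength and SD.

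The 3-month and later forms are not affected by the optional visit (losses after progression or surgery are a separate matter), and the primary analysis is untouched.

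**What to change.** **Preferred:** state in Section 17.4 that forms from the optional 4–6 week visit will be tabulated descriptively by arm, with the number attending and the reason for the visit, and excluded from the between-arm tests and from the repeated-measures or GEE model. Cost: a sentence in the analysis plan and the loss of one unrepresentative time point.

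**Alternative, if an early comparison is wanted:** collect one QLQ-C30/PAN26 from every randomized patient in both arms at a fixed time counted from randomization, by mail or telephone where no visit is held. The visit, its scan and its labs can stay optional. Cost: slight patient burden and some coordinator time.

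**In either case:** reconcile the Calendar column (4–8 weeks) with Section 7.2 and footnote k (4–6 weeks).
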